8.4 Pharmacokinetics

Plasma concentrations of APR-246 will be measured in Cycle 1, at the timepoints provided in [Table 9](#). Please refer to sections [2.3](#) and [6.4](#), regarding the risk of certain drugs and foods influencing the PK of venetoclax such as grapefruits (see [APPENDIX VII](#)). This is important both for patient safety and for enabling a correct assessment of an unlikely drug-drug interaction between the study drug APR-246 and venetoclax from PK samples.

Table 9. PK Blood Sampling Timepoints for APR-246

APR-246 plasma collection timepoints ^a	Cycle 1			Subsequent Cycles
	D1	D2	D4	D4
Prior to APR-246 infusion	×	×	×	×
At the end of APR-246 infusion	×		×	×
1 hour after the end of APR-246 infusion	×		×	× ^c
3 hours after the end of APR-246 infusion ^b	×			

^a A window of ±15 min applies to each time point.

^b Samples are collected as part of the venetoclax PK sampling scheme below ([Table 10](#)). A single PK sample should be drawn and split into 2 samples for analysis of both drugs at these timepoints.

^c Sample collected between 1 and 3 hours after the end of infusion.

Only in cohorts with venetoclax, plasma concentrations of venetoclax will be measured in Cycle 1, at the timepoints provided in [Table 10](#), and then prior to venetoclax administration on Day 4 of Cycles 2 – 5 ([Table 11](#)).

Table 10. PK Blood Sampling Timepoints for Venetoclax in Cycle 1

Venetoclax plasma collection timepoints	D1	D2	D22	D23
Prior to venetoclax administration ^a	×	×	×	×
2 hours following venetoclax administration ^b	×		×	
3 hours following venetoclax administration ^c	×		×	
4 hours following venetoclax administration ^d	×		×	

6 hours following venetoclax administration ^e	×		×	
8 hours following venetoclax administration ^f	×		×	

^a Baseline sample collected prior to venetoclax administration. On Day 1, it is recommended that venetoclax is given 1 hour after the start of APR-246 infusion (± 10 min), following a meal that will start approximately 15 minutes after initiation of APR-246 infusion. On Day 1, the baseline sample prior to APR-246 infusion can be split into two samples and used as pre-dose sample for venetoclax as well.

^b 3 hours following initiation of APR-246 infusion on Day 1 (± 15 min)

^c 4 hours following initiation of APR-246 infusion on Day 1 (± 15 min)

^d 5 hours following initiation of APR-246 infusion on Day 1 (± 15 min)

^e 7 hours following initiation of APR-246 infusion on Day 1 (± 15 min). This blood draw is also used for the 3rd sample for APR-246 measurements ([Table 10](#); 1 hour after EOI).

^f 9 hours following initiation of APR-246 infusion on Day 1 (± 30 min). This blood draw is also used for the 4th sample for APR-246 measurements ([Table 10](#); 3 hours after EOI)

Table 11. PK Blood Sampling Timepoints for Venetoclax in Cycles 2-5

Venetoclax plasma collection timepoints	Day 4
Prior to venetoclax administration ^a	×

8.5 Electrocardiographic Assessment

[Table 12](#) describes the routine ECG requirements from screening through Cycle 4:

Table 12. ECG Assessment Requirements

Time Point	ECG, number	Timing
Baseline/Screening	TriPLICATE	Must be within 28 days of C1D1
Cycle 1, Days 1-4	TriPLICATE	Pre-dose; Post dose (6 hrs. after start of infusion; ± 30 min)
Cycles 2+, Day 1	TriPLICATE	Pre-dose

If repeated QTcF measurements show a stable QTcF < 450 msec, or if QTcF remains stable within the interval of 450–469 msec with no significant change at the EOI during several cycles of treatment, reducing the number of ECGs performed in the study may be discussed with the Medical Monitor.

If a patient starts treatment with another medication known to prolong QT interval at any time during the study therapy, an additional pre- and post-dose (6 hours after start of infusion, ± 30 min) ECG should be performed on the next treatment day.

Please consult Section [6.3.1](#) for additional requirements for proceeding with treatment with APR-246.

8.6 **TP53 Testing**

Patients are enrolled based on the central lab result confirming at least one *TP53* mutation not defined as benign or likely benign (see Laboratory Manual for mutation algorithm) in the bone marrow aspirate sample. The central peripheral blood sample may be used for enrollment in the event a *TP53* mutation is not detected in the bone marrow aspirate sample or if the bone marrow aspirate cannot be obtained due to a dry tap.

If local *TP53* mutation and/or p53 IHC results become available before central *TP53* mutation results, enrollment may be made based on local results with Medical Monitor approval.

9.0 STATISTICS

Demographic data and disease-related characteristics will be summarized using descriptive statistics (count and percent, mean, median, standard deviation, minimum, maximum). Continuous variables will be presented by *n*, mean, median, standard deviation and range (minimum and maximum), and categorical variables will be presented by count and percentage of patients as appropriate. Data will be presented by each dose cohort in safety lead-in dose-finding portion and by each treatment arm and dose cohort in the expansion portion. All patient data, efficacy and safety data will be summarized.

9.1 **Sample Size**

This trial assumes a sample size of 12–36 patients (6–18 patients for each cohort) in the safety lead-in portion of the study and approximately 70 patients in the expansion portion of the study.

In expansion cohorts 2 and 5, Simon's two-stage "minimax" design will be used with alpha level of 0.05 and power of 80%. The null response rate will be set to 20% and the target response rate will be 40%. At the first stage if more than 4 responders in 18 patients observed, then the cohort will be continued to enroll another 15 patients in the second stage. A total of 11 responders or more in 33 patients will indicate the response rate is higher than the null response rate.

9.2 Analysis Populations

Safety population: Patients will be evaluable for safety if they receive at least one dose of APR-246 with venetoclax and/or azacitidine. The safety population will be used to summarize exposure and safety parameters.

DLT-evaluable population: All patients who either experienced a DLT during first 4 weeks (Cycle 1) of the study treatment or received $\geq 80\%$ of scheduled Cycle 1 dose of APR-246 in combination with venetoclax and/or azacitidine and did not experience a DLT. Any individual patient who is not evaluable for DLT will be replaced by a new patient through additional patient enrollment.

Efficacy evaluable (EE) population: All patients who complete at least one treatment cycle of APR-246 in combination with venetoclax and/or azacitidine and who have at least one post-treatment clinical response assessment. Patients who fail to complete one treatment cycle will also be considered EE if they show clear evidence of clinically significant disease progression. The EE population will be the secondary analysis population for efficacy.

Pharmacokinetics (PK) population: Patients will be evaluable for pharmacokinetics if at least one post-dose sample for PK evaluation has been obtained.

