Each cohort will enroll up to 6 patients. DLT will be assessed after three patients have been enrolled in respective cohort and the last enrolled patient has completed the 4-week safety assessment period (i.e., one cycle of combination regimen). A patient that discontinues therapy during Cycle 1 without DLT is considered evaluable for the purpose of safety only if at least 80% of scheduled doses of APR-246 in combination with venetoclax and/or azacitidine were administered in the first cycle. At the first dose level of 4.5 g/day of APR-246, if ≤1 patient out of 3 experiences a DLT, 3 additional patients will be enrolled. If ≤1 patient out of 6 experiences DLT, the dose level (4.5 g/day of APR-246) will be deemed the RP2D for that cohort. If ≥2 patients out of the total 3–6 patients in the cohort experience DLT, the study will continue enrollment at Dose Level -1 (4.0 g/day of APR-246). If ≤1 patient out of 6 experiences DLT at this dose level, the dose level (4.0 g/day of APR-246) will be deemed the

RP2D for that cohort. If ≥ 2 patients out of the total 3 – 6 patients at that dose level experience DLT, the study will continue enrollment at Dose Level -2 (3.5 g/day of APR-246). If ≤ 1 patient out of 6 experiences DLT at this dose level, the dose level (3.5 g/day of APR-246) will be deemed the RP2D for that cohort. If ≥ 2 patients out of the total 3–6 patients at this dose level experience DLT, no additional patients will be enrolled at this dose. The trial will be halted, and the DRT will consider potential future dosing modifications.

Table 2. APR-246 Dose Levels

Dose Modification	APR-246 Dose
Starting Dose Level (DL)	APR-246 4.5 g/day 1.5 g (for first 45 minutes) + 3.0 g (for 5 hours 15 minutes)
Dose Level Reduction -1 (DL-1)	APR-246 4.0 g/day 1.33 g (for first 45 minutes) + 2.67 g (for 5 hours 15 minutes)
Dose Level Reduction -2 (DL-2)	APR-246 3.5 g/day 1.17 g (for first 45 minutes) + 2.33 g (for 5 hours 15 minutes)

The expansion portion will begin once the RP2D of APR-246 in combination with venetoclax and/or azacitidine have been determined in order to assess the antitumor activity of these combinations. Approximately 70 patients will be enrolled in up to five cohorts, as outlined in [Table 3](#):

Table 3. Study Treatment and Prior Therapy by Cohort

Cohort	Disease	Study Treatment	Prior Therapy Permitted						
			VEN	HMA	LDAC	APR-246	SCT	IC	
Safety Lead-In Cohorts									

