6.1.1 APR-246

APR-246 is administered as a 6-hour IV infusion daily on Days 1–4 of each 28-day cycle. APR-246 fixed dose is 4.5 g. APR-246 is administered in a 2-step infusion:

Step 1: Loading dose of 1.5 g for the first 45 minutes (\pm 2 min)

Step 2: Maintenance dose of 3 g over 5 hours 15 minutes (\pm 30 min)

In each portion of the study, if patients develop intolerable toxicity(ies) to APR-246 in combination with venetoclax and azacitidine, the dose of APR-246 may be reduced (please consult Section 4.1 and [Table 2](#)).

APR-246 vials are to be stored at 2-8°C (35.6-46.4°F). At the pharmacies and at the study centers, the prepared APR-246 study product (diluted in sodium chloride solution) is to be stored at not more than 25°C. The infusion should be completed within 24 hours from the time of preparation.

Detailed instructions on vial concentration, preparation and dispensing can be found in the Pharmacy Binder. The infusion timing, including start/stop times and the time of rate change, must be recorded.

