6.1.4 Dose-Limiting Toxicity

An event will be considered a DLT per NCI CTCAE version 5.0 criteria if it occurs within 4-week safety assessment period (Cycle 1 of study treatment) and meets at least one of the criteria below:

- Absolute neutrophil count (ANC) not recovering to $>0.5 \times 10^9/L$ and/or platelets not recovering to $>25 \times 10^9/L$ by day 42 of study treatment in the absence of active leukemia/myelodysplasia;
- Grade ≥ 3 nausea/vomiting/diarrhea or CNS toxicity that does not resolve to Grade ≤ 1 within 7 days despite treatment interruption and maximum medical therapy;
- Treatment-related non-hematological Grade ≥ 3 toxicity that does not resolve to Grade ≤ 1 .

A DLT will be considered related to the study treatment unless there is a clear, alternative explanation for the AE. A \geq Grade 3 metabolic or electrolyte abnormalities that is not clinically significant and is adequately controlled within 72 hours is not to be considered DLT. A tumor lysis syndrome that responds to therapy and resolves within 72 hours is not to be considered DLT.

Additionally, AEs that meet the above criteria, but occur after the DLT evaluation period will not be defined as DLTs, but will be reported as AEs/Serious Adverse Events (SAEs) and will be reviewed across all cohorts during the study to help determine the AE profile. A patient

that discontinues therapy during Cycle 1 without DLT is considered evaluable for the purpose of safety only if at least 80% of doses of APR-246 in combination with venetoclax with and without azacitidine were administered in the first cycle.

Patients who are tolerating APR-246 in combination with venetoclax and/or azacitidine, will not have to discontinue dosing prematurely due to the occurrence of DLTs in another patient in the same cohort, unless decided by the DRT. If requested by the Investigator, depending on the nature of the DLT and patient status, the DRT and the Sponsor may allow a patient to continue with study treatment at a reduced dose.

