6.3 Supportive Management

6.3.1 APR-246

This section outlines the requirements for proceeding with treatment with APR-246, and the protocol rules for APR-246 dose modification due to toxicity.

At screening, 12-lead ECGs should be collected in triplicate to confirm QT interval does not exceed 470 msec in patients without pre-existing bundle branch block (BBB) and/or pacemaker. For patients with pre-existing BBB and/or pacemaker, QTcF at screening should not exceed baseline reading known per medical history. QT interval must be calculated from a mean of all three ECG readings using Fridericia's correction ($QTcF = QT/RR^{0.33}$).

During Cycle 1 ECG should be collected in triplicate prior to infusion of APR-246 and at the end of infusion (EOI) of APR-246 (6 hours after start of infusion, ± 30 min) on Days 1–4. QTcF must be calculated from a mean of all three ECG readings to confirm it does not exceed 470 msec in patients without pre-existing BBB and/or pacemaker. For patients with pre-existing BBB and/or pacemaker, QTcF measurements in Cycle 1 should be at or below values recorded during screening period.

If a pre-dose ECG shows $QTcF \geq 470$ msec, the QTc reading should be confirmed by manual assessment using Fridericia's correction ($QTcF = QT/RR^{0.33}$). Serum concentrations of electrolytes should be monitored and corrected, if necessary. Additionally, concomitant medication should be reviewed and adjusted, if necessary. ECG may be repeated at any time, including the same day. APR-246 may only be administered when QTcF has returned to <470 msec. If APR-246 is given on the same day, procedures outlined in the Schedule of Study Evaluations ([Table 8](#)) must be followed. If APR-246 cannot be administered on the same day, that dose must be omitted from the cycle.

If there is a significant change in QTcF, defined as either: a) increase >60 msec from baseline (or pre-dose), or b) increase to an absolute value ≥ 501 msec, i.e. consistent with NCI CTCAE Grade 3 QTc prolongation, QTc prolongation must be confirmed by a manual assessment of the ECG, and using Fridericia's correction ($QTcF = QT/RR^{0.33}$). If confirmed, the APR-246 therapy should be interrupted until a cause (electrolyte disorders or an effect of a concomitant medication) has been identified and addressed, and QTcF has returned to <470 msec. If all other causes for clinically significant QT interval prolongation are excluded, APR-246 must be permanently discontinued.

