6.3.2 Management of CNS Adverse Events

If a patient reports any clinical AE of any grade during the administration period of APR-246 that could be considered to originate from the CNS (e.g. dizziness, vertigo, nausea) then the patient will be given a rescue medication as per the institutional standard of care.

Dose modifications of APR-246 have been successfully used to manage potential CNS effects occurring during the infusion (Table 4). For any clinical AE Grade ≥ 3 , the infusion of APR-246 should immediately be stopped, and if all symptoms resolve to CTCAE \leq Grade 1 within 2 hours, the infusion of APR-246 may be resumed at the same infusion rate. If the same symptoms do occur or increase in severity during re-challenge the infusion of APR-246 should be stopped.

If the event lasts longer than 2 hours, then the APR-246 infusion should be discontinued for that day, the remaining drug should be discarded.

Table 4. Management of CNS Adverse Events (Dizziness, Dyskinesia and Ataxia)

Worst toxicity	Dose Modifications for APR-246
Grade 1	Maintain dose level
Grade 2	If resolved to \leq Grade 1 with medical therapy, continue same dose level If not resolved despite treatment interruption and maximal medical therapy, stop infusion and \downarrow 1 dose level for subsequent dose
Grade \geq 3	Stop infusion and give medical therapy. If resolved (to \leq Grade 1) with medical therapy, infusion may continue at the Investigator's discretion. \downarrow 1 dose level for subsequent dose
Grade 4	Permanently discontinue patient from APR-246.

In prior studies, prochlorperazine 10 mg orally tid (three times daily) has been reported to be an effective treatment that may also be used prophylactically. When prochlorperazine is used prophylactically, start the day prior to the Day 1 and continue 10 mg tid to day 4 (as needed). The US label for prochlorperazine does not list QT interval prolongation as a known risk associated with use of this drug.

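### The DLT definition omits resolving Cycle 1 events for which the protocol permanently stops APR-246, so the fewer-than-2-of-6 RP2D rule cannot register them, whether the patient is replaced or kept

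*Combined protocol and SAP*

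**What the plan says.** **DLT criteria (Section 6.1.4; Synopsis, Statistics).** There are three:

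- failed count recovery by Day 42;
- Grade 3 or higher gastrointestinal or CNS toxicity not back to Grade 1 or lower within 7 days;
- treatment-related non-haematological Grade 3 or higher toxicity that does not return to Grade 1 or lower, with no time stated.

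None mentions stopping APR-246 or losing a dose. One exemption reads: "A tumor lysis syndrome that responds to therapy and resolves within 72 hours is not to be considered DLT".

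**Mandatory stops and omissions.** For confirmed QTcF prolongation, Section 6.3.1 says: "If all other causes for clinically significant QT interval prolongation are excluded, APR-246 must be permanently discontinued". Where a pre-dose QTcF has not come back under the limit: "If APR-246 cannot be administered on the same day, that dose must be omitted from the cycle". For Grade 4 CNS events, Table 4 in Section 6.3.2 says: "Permanently discontinue patient from APR-246".

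**Evaluability.** Section 9.2 requires a patient without a DLT to have had at least 80% "of scheduled Cycle 1 dose of APR-246 in combination with venetoclax and/or azacitidine and did not experience a DLT". Anyone else is covered by: "Any individual patient who is not evaluable for DLT will be replaced by a new patient through additional patient enrollment". No exception is made for doses missed because of toxicity. Section 4.1 is worded differently: "A patient that discontinues therapy during Cycle 1 without DLT is considered evaluable for the purpose of safety only if at least 80" per cent, a figure that there refers to the number of doses given. It covers only patients who discontinue.

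**Decision rule and result.** The RP2D is the dose at which fewer than 2 of 6 patients have a DLT (Sections 6.1.5 and 9.3.1). The Synopsis reports that both lead-in cohorts finished with six patients each, no DLTs and an RP2D of 4.5 g/day.

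**The concern.** DLTs and the RP2D are primary endpoints, and the RP2D opens an expansion of about 70 patients. A 3 + 3 rule protects patients only against what it counts as an event. Here the protocol treats some events as serious enough to end APR-246 for good, while its DLT definition may treat the same events as nothing. Section 6.1.4 even allows a patient with a DLT to continue at a reduced dose in some circumstances, so an event that forces a permanent stop can carry less weight in dose finding than one that does not.

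The evaluability rule does not repair this. Depending on how the 80% is read, the patient either leaves the DLT analysis or stays in it without an event. A reader told that no DLTs occurred in six patients cannot tell whether other patients started and were replaced after failing to tolerate APR-246.

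**Working it through.** **Plan's own figure.** Lead-in size: 2 cohorts × 6 patients × 1 to 3 dose levels = 12 to 36, or 6 to 18 per cohort. This matches Section 9.1 exactly and leaves no room for replacements.

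**Step 1: can a mandatory stop escape the DLT criteria?**

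| Event | Required action | DLT status |
|---|---|---|
| Confirmed significant QTcF prolongation, other causes excluded | Permanent stop (6.3.1) | Only the third criterion could apply; not met if it resolves |
| Grade 4 CNS event (Table 4) | Permanent stop (6.3.2) | Not met if back to Grade 1 or lower within 7 days |

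**Step 2: what does the 80% rule do with the patient?** Section 6.1.1 gives four Cycle 1 doses: "APR-246 is administered as a 6-hour IV infusion daily on Days 1–4 of each 28-day cycle".

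- *Applied to APR-246 by doses:* one lost, 3/4 = 75%; stopped after Day 1, 1/4 = 25%. Both fail, and the patient is replaced.
- *Applied to APR-246 by amount:* 4 × 4.5 g = 18 g and 80% is 14.4 g, so up to 3.6 g may be lost. A whole dose (4.5 g) fails. An infusion stopped just after the 1.5 g loading step leaves (13.5 + 1.5)/18 = 83.3%, which passes.
- *Pooled over drugs* (28 venetoclax days assumed, other drugs given in full): the triplet has 4 + 28 + 7 = 39 doses. One APR-246 dose received gives 36/39 = 92%, so the patient is evaluable with no DLT. In the doublet, 29/32 = 91%.

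**Step 3: what can the RP2D rule see?** For event probability p per patient, the chance that a dose level passes is

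P(X ≤ 1 of 6) = (1 − p)^6 + 6p(1 − p)^5.

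The sequential rule (at most 1 of 3, then at most 1 of 6) gives the same value. Let d be the protocol-defined DLT rate and t the rate of resolving, toxicity-driven APR-246 loss that is not a DLT. The documents give neither, so both are assumptions. Use p = d if such patients are kept as non-events, p = d/(1 − t) if they are replaced, and p = d + t if the events counted.

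| d | t | Kept as no DLT | Replaced | Counted |
|---|---|---|---|---|
| 0 | 20% | 100% | 100% | 65.5% |
| 0 | 30% | 100% | 100% | 42.0% |
| 0 | 40% | 100% | 100% | 23.3% |
| 10% | 10% | 88.6% | 86.3% | 65.5% |
| 10% | 20% | 88.6% | 83.3% | 42.0% |
| 10% | 30% | 88.6% | 79.3% | 23.3% |

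With replacement, the expected number treated to obtain six evaluable patients is 6/(1 − t): 6.7, 7.5 and 8.6 at t = 10%, 20% and 30%.

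**The case against.** **The events are not lost to the trial.** Related adverse events are themselves a primary endpoint (Section 9.3.1). The safety population needs only one dose (9.2), and events leading to dose modification or discontinuation are summarised (9.4). The Data Review Team looks at adverse events as well as DLTs when it recommends the RP2D (6.1.5). This stands and limits the point: the gap is in the DLT and RP2D endpoints, not in safety reporting. But none of these routes applies the 2-of-6 threshold.

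**Replacement does not lower the DLT rate.** A reader might infer that replacing these patients biases the DLT proportion downward. It does not: they have no DLT as defined, so removing them raises the proportion from d to d/(1 − t) and makes passing slightly harder. The shortfall exists only relative to a count in which treatment-ending toxicity is an event. The root is the DLT definition; replacement adds that such patients drop out of sight.

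**One lost dose need not exclude a patient.** That inference holds only if the 80% is specific to APR-246 and a whole dose is lost.

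**The 72-hour exemptions do not show a contradiction.** The tumour lysis exemption looks redundant if any resolved event is already outside the third criterion, but redundancy is not contradiction. The electrolyte exemption turns on clinical significance and control, not on resolution, so it keeps a function. The third criterion can also be read as unresolved at the end of the four-week period. The text does not say so.

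**The rates are assumed.** This is correct. The table shows the size of the blind spot for given rates, not evidence that those rates apply.

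**Conclusion.** The point holds in a limited form. The text allows a Cycle 1 event to require permanent discontinuation of APR-246, resolve, and count as nothing in the RP2D decision. This follows under both readings of the 80% rule; the reading decides only whether the patient is replaced or kept as a non-event. Related Grade 3 or higher non-haematological events that never resolve are still DLTs, so the endpoint can miss such toxicity but does not miss all of it.

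The size depends on unknown rates. At an assumed d = 10% and t = 20%, a dose level passes with probability 83% to 89% as written, against 42% if these events counted.

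A reader might conclude that the declared RP2D of 4.5 g/day is wrong. The documents do not support that. They report no DLTs in six patients per cohort and do not say how many started, whether anyone was replaced, or why. What is missing is the information needed to judge the result.

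**What to change.** 1. Reconcile the DLT criteria (Section 6.1.4; Synopsis, Statistics) with the mandatory discontinuation rules in Sections 6.3.1 and 6.3.2, including the missing time for resolution in the third criterion. The clinical content is for the sponsor to decide.
2. Reconcile the 80% wordings: doses, in patients who discontinue (Synopsis, Study Design; Sections 4.1 and 6.1.4), against dose, in every patient without a DLT (Synopsis, Analysis Populations; Section 9.2). State whether the threshold is per drug or pooled.
3. State that patients who miss Cycle 1 APR-246 doses because of treatment-related toxicity are not removed by replacement from the reported tolerability analysis.
4. For each lead-in cohort, report the number treated, the number replaced and the reasons. Beside the protocol-defined DLT rate, give a sensitivity count over all treated patients in which toxicity-driven Cycle 1 APR-246 discontinuation or dose omission is an event. Enlarging the denominator alone would only dilute the rate.

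The reported lead-in DLT result should stand as defined; redefining a primary endpoint after its result is known would create a new problem. The cost is wording changes and some reanalysis of existing Cycle 1 dosing and adverse-event data. The sensitivity count is post hoc for the completed lead-in and should be labelled so, and the tolerability figure may become less favourable.
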